8.0 REGISTRY POPULATION

The registry population includes patients with one or more soft tissue liver lesions of any size, location, or shape who underwent or will undergo a MWA procedure with the NEUWAVE Microwave Ablation System.

9.0 INVESTIGATOR RESPONSIBILITIES

9.1 Good Clinical Practices

An Investigator is responsible for ensuring that this registry is conducted in accordance with the ethical principles that have their origin in the Declaration of Helsinki and that are consistent with the ICH GCP, the signed Clinical Trial Agreement, this Protocol, the institution’s IRB/EC policies and procedures, and applicable regulatory requirements.

Prior to the initiation of this clinical registry at each site, the responsible Principal Investigator will approve this Protocol by signing the signature page. This signature confirms that the clinical registry will be performed in compliance with this protocol.

The following documents must be provided to the Sponsor prior to registry start:

1. A copy of the formal written notification to the Investigator regarding approval of the protocol by an IRB/EC that is in compliance with regulatory guidelines.

2. A copy of the IRB/EC approved ICF or ICF waiver and other adjunctive materials (e.g., advertising) to be used in the registry, including written documentation of IRB/EC approval of these items.
3. Name and address of the IRB/EC, and a current list of the IRB/EC members. If accompanied by a letter of explanation from the IRB/EC, a general statement may be substituted for this list, or a general assurance number.
4. Applicable local regulatory documentation.
5. Signed and dated protocol Investigator Signature page.
6. Signed confidentiality agreement between the Investigator and the Sponsor.
7. Signed and dated clinical trial agreement, including financial agreement.
8. Up-to-date signed and dated curriculum vitae for each investigator and sub-investigator.
9. Statement of Investigator.

Other documents may also be required prior to the registry and during the course of the registry.

9.2 Institutional Review Board/Ethics Committee

Participating investigators will ensure that this protocol, corresponding ICF/Waiver, or protocol amendments, and if applicable, any other written information provided to the patients that assist in the decision to participate are reviewed by an IRB/EC that complies with governmental requirements. The approving IRB/EC will be responsible for the initial and continuing review and approval of this registry. Participating investigators will be required to promptly report to the IRB/EC as required by the IRB's/EC's policies. Additionally, investigators will be required to refrain from making any changes in the protocol without Sponsor and IRB/EC approval of an amended protocol, except where necessary to eliminate apparent immediate hazards to registry patients or others.

9.3 Patient Information and Consent

To minimize selection bias, sites should attempt to identify and approach all eligible patients for consent who were ablated or will be ablated for soft tissue liver lesions using the NEUWAVE Microwave Ablation System or the NEUWAVE Microwave Ablation System with Ablation Confirmation. Patients who had liver ablations with NEUWAVE prior to consent are eligible to participate as retrospectively enrolled patients. Retrospective patients can be fully retrospective (all protocol visits have occurred prior to the date of ICF/waiver) or can have some prospective follow-up (applicable protocol visits occur after signing the ICF).

The informed consent process involves the investigator or delegated staff to complete the following activities: giving a patient adequate information concerning the registry, providing adequate time for the patient to consider all available options, responding to the patient's questions, ensuring that the patient has comprehended this information, and finally, prior to a

patient's participation in this registry, an ICF will be signed and dated by the patient and person who conducted the consent discussion. All prospective patients in this registry should be completely informed about the purpose, risks, benefits, and other pertinent details of this registry. The informed consent process is careful to avoid the perception of any coercion or undue influence on, or inducement of, the patient to participate, and does not waive or appear to waive the patient's legal rights. The ICF is presented in native, non-technical language that is understandable to the patient. The patient will be provided with a copy of the signed ICF. Completely retrospective patients will need to have an ICF waiver in place prior to having his or her data collected.

The ICF and any other written materials provided to the patient to assist in the decision to participate must be revised whenever new information becomes available that may be relevant to their willingness to participate or continue participation in this registry. Revision to the ICF and other written materials will receive IRB/EC approval before implementation. Each patient required to sign an amended ICF will receive a copy of the signed ICF. All original signed amended ICFs will also be kept within the patient's medical record.

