7.0 REGISTRY DESIGN

7.1 Overall Registry Design and Plan – Description

This is a multicenter, observational registry that follows patients for a total of 5 years from the date of the first liver ablation procedure with the NEUWAVE Microwave Ablation System. The data gathered from participating sites will be available to be analyzed to develop ablation parameter guidance for ablation approaches under varying patient liver tissue conditions and liver lesions.

This is an “umbrella registry,” which was included as an optional component in other NEUWAVE studies; hence, data from consenting patients who are or will be enrolled in other NEUWAVE soft tissue liver lesion ablation studies will be included in this registry. All other patients will be enrolled and followed prospectively, enrolled retrospectively with prospective, longitudinal follow up, or enrolled retrospectively with all retrospective follow up.

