7.3 Inclusion Criteria

1. Patients who underwent or are scheduled to undergo a microwave ablation of one or more liver lesions with the NEUWAVE Microwave Ablation System per the device's Instructions for Use (IFU).
2. Patients with signed informed consent (or waiver approved by IRB/EC) who are willing to comply with the assessment schedule, and willing to have data included in the database.
3. Patients \geq 22 years old at the time of informed consent (or waiver approved by IRB/EC).

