18.3 Patient Information and Consent

Regulations concerning the protection of patients require that informed consent be obtained, or waiver approved by the IRB/EC where applicable, before a patient may participate in any clinical registry. For this registry, a patient must be consented or waiver approved by the IRB/EC before completing any registry specific procedures. Screening information that are part of SOC procedures may occur and be collected prior to consent, but the data may not be collected for registry purposes until the informed consent form (ICF) has been signed by the patient or waiver from the IRB/EC is received. A patient who signs the consent, or waiver is received, is considered enrolled.

An IRB/EC approved informed consent or waiver, where applicable, must be sought from each patient and must be appropriately documented in the patient's medical record. It is the Investigator's responsibility to obtain written informed consent from prospective patients or retrospective patients with prospective follow-up prior to registry-specific procedures. The Investigator may delegate this responsibility, if appropriately documented.

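### The definition of fully retrospective leaves patients who died before enrollment without a clear class, and a literal reading would select the waiver cohort on 5-year survival

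*Protocol*

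**What the plan says.** Protocol section 7.1 describes patients who enter after their ablation as "enrolled retrospectively with prospective, longitudinal follow up, or enrolled retrospectively with all retrospective follow up". Section 9.3 is the only place that defines these two classes: "Retrospective patients can be fully retrospective (all protocol visits have occurred prior to the date of ICF/waiver) or can have some prospective follow-up". It explains the second class as one in which "applicable protocol visits occur after signing the ICF". It then links the first class to the waiver: "Completely retrospective patients will need to have an ICF waiver in place prior to having his or her data collected". Section 18.3 makes the investigator responsible to "obtain written informed consent from prospective patients or retrospective patients with prospective follow-up prior to registry-specific procedures".

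The Schedule of Assessments runs to Visit 14, at 54 to 60 months. Inclusion criterion 2 (section 7.3) covers patients with a signed consent or an approved waiver "who are willing to comply with the assessment schedule, and willing to have data included in the database".

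Section 9.3 also states a broad intent. "Patients who had liver ablations with NEUWAVE prior to consent are eligible to participate as retrospectively enrolled patients", and "To minimize selection bias, sites should attempt to identify and approach all eligible patients for consent who were ablated or will be ablated".

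In the SAP, section 6 puts everyone who met the eligibility criteria and was treated with the device into the full analysis set (FAS). Section 8.6 estimates overall and recurrence-free survival in that set by Kaplan-Meier up to 60 months.

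**The concern.** Waiver patients are the one retrospective group who need not be alive at enrollment. They are therefore the route by which early deaths among past ablations could reach the registry. If that route is open only to patients whose whole visit schedule took place, it closes to the patients whose outcomes would lower the survival estimate.

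Consider a patient ablated three years before a site opened who died at 14 months. This patient cannot sign a consent form, so the class with prospective follow-up is closed. Visits after month 14 never happened, so on a literal reading the fully retrospective class is closed too. A patient who was lost and cannot be re-contacted is in the same position until the 60-month window has passed.

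A cohort admitted on that basis is selected on survival, which is itself an endpoint. It would be pooled with prospectively enrolled patients, and nothing in the planned output would separate the two.

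**Working it through.** The plan gives no survival rate, no share of retrospective patients and no sample size calculation, so there is no figure of its own to reproduce. The check is a comparison of sections, followed by an illustration on assumed inputs.

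**Step 1: the literal reading.** The two definitions in section 9.3 use different words. The class with prospective follow-up speaks of applicable visits; the fully retrospective class speaks of all of them. Section 7.7 lists death and loss to follow-up among the reasons why participation ends before the registry is completed. On these terms a patient who died at month 14 has not had all visits. No sentence in either document says how to class a patient who died before enrollment.

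**Step 2: the looser reading.** Several places fit a reading in which no visit remains to be done:
- Protocol sections 7.1 and 17.2 and SAP section 1.2 name the class by its follow-up being wholly retrospective, with no completion condition.
- Protocol section 17.2 and SAP section 1.2 describe follow-up of up to 5 years.
- Protocol section 14.0 says that assessments not completed in retrospective patients are not deviations.
- The All Enrolled Set (SAP section 6) asks only for consent or a waiver.
- No inclusion or exclusion criterion requires survival to year 5.

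Both readings are tenable, so practice may vary between sites.

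**Step 3: inclusion criterion 2.** The clause on willingness to follow the schedule is attached to waiver patients as well. A deceased patient cannot meet it, and the FAS requires that the criteria be met. Taken literally, though, it fails for every waiver patient who is never asked, including one who completed year 5. It adds to the uncertainty but does not by itself pick out survivors.

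**Step 4: would the SAP show the effect?** Section 8.6 states no entry time other than the ablation. Section 8.8 has subgroups by disease type and by use of the confirmation software, and only for the primary endpoints. Section 8.7 plans no sensitivity analysis. Nothing separates patients by enrollment class.

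**Step 5: illustration of size.** Let f be the share of the FAS that entered by waiver under the literal reading, and S the true 5-year overall survival in everyone else. Both are assumptions. The waiver group has no deaths before Visit 14, so its estimate is 100% by construction. With everyone else fully followed:

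Pooled survival = f × 1 + (1 − f) × S, and bias = f × (1 − S).

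For S = 50%:
- f = 10%: 0.10 + 0.90 × 0.50 = 55%
- f = 20%: 0.20 + 0.80 × 0.50 = 60%
- f = 30%: 0.30 + 0.70 × 0.50 = 65%

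Over a wider range of assumptions:

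| S | f = 10% | f = 25% | f = 50% |
|---|---|---|---|
| 30% | 37.0% | 47.5% | 65.0% |
| 50% | 55.0% | 62.5% | 75.0% |
| 70% | 73.0% | 77.5% | 85.0% |

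The bias runs from 0.10 × 0.30 = 3 points to 0.50 × 0.70 = 35 points. Recurrence-free survival is also pushed upward, because deaths count as events there. The formula does not size that effect, since survivors can still have recurrences.

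**The case against.** The strongest reply is that a parenthesis in a consent section is not an eligibility rule. Eligibility is set in sections 7.3 and 7.4, where a past ablation is enough. Section 11.1 includes data from all consented or waived patients who have been ablated. Section 9.3 itself asks sites to approach everyone eligible in order to limit selection bias. On that view a sensible site would enter a deceased patient as fully retrospective.

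Much of this stands, and it rules out three stronger conclusions that a reader might draw:
- **That the waiver cohort is restricted by rule to 5-year completers.** That follows only where a site applies the literal wording. The sections in step 2 permit the other reading.
- **That every patient lost to follow-up is shut out.** A lost patient who is alive, re-contacted and still within 5 years can sign and continue prospectively, and section 7.7 allows a returning patient's status to be updated. One whose 60-month window has passed can be read as having no visit left. The gap concerns patients who died or cannot be re-contacted.
- **That delayed entry would be useless.** Completers who enter at about year 5 would add no time at risk before then, so the inflation would disappear. What would be lost is their information, and the missing deaths would still be missing.

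The reply does not show that the looser reading is the one sites used. An instruction to approach patients for consent cannot reach someone who has died, and the general statements do not say how that person is to be classed.

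**Conclusion.** The point holds as an ambiguity with a one-directional risk. Section 9.3 does not place a patient who died, or was lost beyond contact, before year 5 and before enrollment. The literal reading leaves such patients out; the looser reading lets them in. Where the literal reading is applied, pooled overall and recurrence-free survival are biased upward, and the SAP has no analysis that would show it.

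The size is unknown. The figure of 5 points per 10% share rests on an assumed 5-year survival of 50%, complete follow-up of everyone else, and literal application at the sites concerned. If sites used the looser reading throughout, this source of bias is absent. The change is worth making because it is cheap and serves the aim of limiting selection bias that section 9.3 states.

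**What to change.** 1. **Protocol section 9.3.** Define the class as: *fully retrospective – no applicable protocol visit remains at the ICF/waiver date, whether through completion of Visit 14, death, or loss to follow-up.*
2. **Inclusion criterion 2 (section 7.3 and the protocol summary).** State that willingness to comply with the assessment schedule applies only to patients with prospective follow-up.
3. **Site instruction.** Ask each site that uses a waiver to enter all eligible ablated patients for the calendar period it opens, including those who died or were lost. The SAP is dated 30 October 2025 and the documents do not give the enrollment status. If enrollment has closed, establish and document how each site applied the definition.
4. **SAP section 8.6.** Report overall and recurrence-free survival by enrollment class (prospective, retrospective with prospective follow-up, fully retrospective). Use delayed entry at the consent date for patients who had to be alive to consent.

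The cost is a protocol wording change, a site memo, some extra tables, and limited chart abstraction for deceased or lost patients at waiver sites. Reported survival may become less favourable.

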10.0 REGISTRY INTERVENTIONS

There is no intervention, beyond necessary, standard, clinical care in this registry.

11.0 REGISTRY PROCEDURES AND EVALUATIONS

11.1 Procedure Description(s)

Pseudoanonymized data from all patients who provide consent (or an IRB approved ICF waiver), and who are undergoing or have undergone microwave ablation of one or more soft tissue liver lesions using the NEUWAVE Microwave Ablation System will be included in the registry's clinical database. The ablation will be performed in accordance with the institution's SOC for microwave ablation and per the device's IFU.

11.2 System Overview

The NEUWAVE Microwave Ablation System has a single 2.45 GHz signal microwave source generator and three (3) independent microwave amplifiers, each capable of producing up to 140W each. Generator power is limited based upon the number of probes selected and the types of probes used. One touch-screen user interface controls the system. The User Interface can be set for either Ablation Mode or Surgical Mode. Up to three (3) microwave ablation probes can be connected to and powered by the system at one time. An intermediate junction box or Power Distribution Module (PDM) reduces system set up complexity.

Cooling System Overview

A CO₂ based cooling system ensures the non-active portion of the probe does not exceed temperature requirements. Additionally, the CO₂ enables the Tissu-Loc™ function, which may be used to adhere or stick the probe in place prior to starting ablation therapy. This function is similar in use to the stick function available on cryogenic ablation systems.

The system uses two (2) CO₂ cylinders (size may vary by market). When a tank in use empties, the system will automatically switch to using the other tank and notify the user to replace the empty tank.

The cooling system regulates the flow of high-pressure CO₂ in a cooling gas tube to the PDM and eventually to the probe. Inside the tip of the probe, the cooling gas tube expands from high pressure to low pressure. As the gas pressure reduces quickly, the Joule-Thompson effect causes the probe shaft to cool. This is used for both the Tissu-Loc™ function and to keep probes at a safe temperature while energy is being delivered to the patient.

The PDM is designed to improve the usability of the system by reducing set-up complexity while also helping to minimize the cabling from the probe to the generator. The PDM also allows a larger, lower-loss cable to be used between the microwave generator and PDM. The increased efficiency of the larger cable and PDM allow more power to be safely sent to the ablation probe without an unsafe heating of the probe cable or handle.

System performance is constantly monitored. The NEUWAVE Microwave Ablation System will automatically discontinue delivering microwave energy in the event of system failures.

NEUWAVE Ablation Probes Overview

NEUWAVE Ablation Probes are provided sterile and are intended for single patient use only. Ablation probes are comprised of a sharp trocar on the end of a cannula, a probe handle, a 1.4-meter cable, and a connector assembly.

Each NEUWAVE Ablation probe contains three (3) temperature measurement sensors that help monitor performance and ensure patient and operator safety.

The NEUWAVE ablation probe assembly contains four (4) main sections: a handle, a cannula, a radiating section, and a faceted tip for insertion.

All NEUWAVE Ablation Probes should be used within their cleared indications.

Most commonly used probes are LK and PR. NEUWAVE LK probes are designed to perform optimally, in terms of efficiently transferring energy into tissue, in liver and kidney tissues.

The antenna of the NEUWAVE PR probe is designed to limit the length of the ablation compared to LK probes for instances when a shorter ablation zone is desired. The NEUWAVE PR probes are designed to produce ablations that quickly encompass the tip of the probe while limiting the overall length of the ablation. NEUWAVE PR probes will enable physicians to ablate smaller lesions while limiting necrosis of adjacent tissue when compared with other NEUWAVE probes.

Refer to the NEUWAVE Microwave Ablation System accompanying documents, such as the IFU, for a list of Warnings and Cautions.

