19.0 DATA HANDLING AND RECORD KEEPING

19.1 Data Elements

The following three categories of data will be captured in the registry database: (1) ablation procedure parameters, (2) patient parameters, and (3) healthcare provider parameters. The complete list of data parameters requested for this registry database are listed below.

1. Ablation procedure parameters:

- a) Procedure type: laparoscopic surgical; open surgical; percutaneous.
- b) Complete procedure duration from start of anesthesia administration (start time) to completion of the procedure (end time).
- c) Ablation duration for each individual ablation attempt (minutes and seconds).
- d) Ablation duration, defined as the time elapsed between first ablation probe puncture and removal of the last probe at the completion of the ablation.
- e) Type of anesthesia used during ablation procedure.
- f) Anatomical location of ablation.
- g) Liver stiffness near ablation site, if obtained prior by ultrasound or MRI.
- h) Smallest ablation margin, if available. Note: if less than 5mm margin, include reason (vessel, duct, location, bowel, other).
- i) Ablation Zone measurement, if available
- j) Use of hydrodissection during ablation procedure.
- k) Type of probe(s) (including serial number).
- l) Number of probes.
- m) Maximum probe temperature, per probe (°C).
- n) Power settings used per probe (Watts).
- o) Constant power vs ramp-up.
- p) Number of probe placement attempts per probe (to get the probe in position).
- q) Number of changes in probe placement throughout the ablation (after energy has been delivered).
- r) Location of probe placement relative to the target lesion (central, peripheral).
- s) Tract ablation (yes/no).
- t) If overlap of coagulation zones, provide overlap, if available.
- u) Needle navigation/placement guidance method used.
- v) Image fusion details, if applicable
- w) Identify if ablation procedure guidance software was used (i.e. for target identification, ablation monitoring, and/or ablation confirmation)
 - If NeuWave ablation confirmation software used, note use of the software, tissue contraction percentage, and the software version
 - If other software, note supplier/manufacturer
- x) If applicable, total number of CT and Xray scans used for the Ablation and total amount of radiation dose
- y) Imaging details (contrast, slice thickness if applicable).

2. Patient parameters:

- a) Patient lesion details at baseline:

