This registry will be open to receiving data from all patients who are ablated with microwave ablation of soft tissue liver lesions using the NEUWAVE Microwave Ablation System. Given that the objective of the registry is to investigate the relationships that exist between the stated clinical outcomes, patient and provider parameters, and microwave ablation (MWA) time and power, no power analysis or sample size determination have been performed given the absence of a specific hypothesis to test.

8 Statistical Analysis Methods

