8.10 Exploratory Analyses

Logistic regression analysis will be utilized to explore the relationship between dichotomous clinical outcomes (technical success and technique efficacy) and ablation procedure, patient, and provider parameters. Significance level of 0.2 will be used for variable selection in a regression model. Cox proportional hazard model will be used for time to event analyses for target lesion recurrence to explore the relationship with ablation procedure, patient, and provider parameters.

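### SAP 8.10 lets a model keep power and drop the probe number and type that limit it, so the power estimate can be confounded in either direction

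*Protocol*

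**What the plan says.** Protocol 11.2 (System Overview) describes "three (3) independent microwave amplifiers, each capable of producing up to 140W each" and then adds: "Generator power is limited based upon the number of probes selected and the types of probes used". It gives no table of limits. The same section links probe type to the lesion: "NEUWAVE PR probes will enable physicians to ablate smaller lesions while limiting necrosis of adjacent tissue".

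Protocol 19.1 collects the relevant items as separate procedure parameters: probe type (item k), "Number of probes" (item l) and "Power settings used per probe (Watts)" (item n).

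SAP section 7 describes the aim as relating outcomes to "patient and provider parameters, and microwave ablation (MWA) time and power". Probe number and type are not named there, although Protocol 5.0 lists them beside time and power.

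SAP 8.10 plans logistic models for technical success and technique efficacy and a Cox model for target lesion recurrence. Each draws on the procedure, patient and provider groups of parameters. The only rule for building them is: "Significance level of 0.2 will be used for variable selection in a regression model". There is no covariate list, forced term, interaction or named selection procedure, and the Cox model has no selection rule of its own. Protocol 17.9 had deferred variable selection and data reduction to the SAP. SAP 8.7 rules out sensitivity analyses.

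**The concern.** Where the limit on power falls as probes are added, a low per-probe setting partly signals a multi-probe procedure. Probe number and type may have their own relation to outcome, both directly and because they follow the lesion. A power coefficient estimated without them mixes the effect of Watts with the effect of configuration.

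The 0.2 rule treats each candidate on its own merits. It can drop probe number or type while keeping power, and the SAP contains nothing to prevent or detect this. Parameter guidance is in the registry's title, and power is one of the two exposures named in SAP section 7, so this coefficient would be among those most used.

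**Working it through.** The plan has no figure to reproduce: it states no effect size, power or sample size calculation. The check asks how far the power coefficient moves when probe number is left out, and how well the 0.2 rule guards against that.

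**From the documents:** power is limited by probe number and type; at most three probes; up to 140 W per amplifier; selection level 0.2; about 1,500 patients.

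**Assumed:** limits per probe, probe mix, settings relative to the limit, and the effects. Probe type and clustering of lesions were not simulated.

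**Set A.** 1,500 patients, 300 replicates, logistic model. Shares of 1/2/3 probes are 50/35/15%, power is uniform over 55-100% of the limit, and the true power effect is 0.30 log-odds per 20 W at fixed probe number.

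The approximate expected coefficient with probe number omitted is

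b(omitted) ≈ b(power) + b(probe) × d, where d = Cov(probes, power) / Var(power).

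For limits of 140/100/70 W:
- Mean probes = 0.50×1 + 0.35×2 + 0.15×3 = 1.65. Mean limit = 70 + 35 + 10.5 = 115.5 W.
- Cov(probes, limit) = 171.5 − 1.65×115.5 = −19.08. Multiplying by the mean fraction 0.775 gives Cov(probes, power) = −14.78.
- Var(power) = 14,035×0.6175 − (115.5×0.775)² = 8,666.6 − 8,012.5 = 654.1. Here 14,035 is the mean squared limit and 0.6175 = 0.775² + 0.45²/12.
- d = −14.78/654.1 = −0.0226 per W, or −0.45 per 20 W.
- With b(probe) = +0.6: 0.30 − 0.27 = 0.03. With b(probe) = −0.6: 0.30 + 0.27 = 0.57.

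The simulation agrees closely. Mean power coefficient with probe number omitted (true 0.30):

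| Assumed limits, 1/2/3 probes | Probe effect −0.6 | −0.3 | 0 | +0.3 | +0.6 |
|---|---|---|---|---|---|
| 140/140/140 W | 0.29 | 0.30 | 0.31 | 0.30 | 0.31 |
| 140/120/100 W | 0.57 | 0.43 | 0.30 | 0.18 | 0.08 |
| 140/100/70 W | 0.61 | 0.46 | 0.30 | 0.16 | 0.04 |

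With probe number in the model as categories, the estimate was 0.30-0.31 in every row and column. At a probe effect of +0.6, power alone met p < 0.2 in 33% (middle row) and 25% (bottom row) of replicates, against 96% and 94% with probe number included. When both were tested jointly, the 0.2 rule kept a truly relevant probe number in 68-100% of replicates with a limit, so it dropped it in up to 32%.

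**Set B.** 1,500 patients, success about 94%, true odds ratio 1.11 per 10 W. This is a weaker effect than in set A, where exp(0.15) = 1.16 per 10 W. Limits are 140/95/65 W (strong) or 140/120/100 W (milder).
- Probe number always omitted, strong limits: odds ratio 1.02 or 0.98 for probe effects of +0.5 or +0.8. With an effect of −0.5, omission raised it to 1.23.
- Probe number tested in the joint model at 0.2: mean odds ratio 1.09-1.13. Coverage of the 95% interval was 81-90% under strong limits and 92-96% under milder ones.
- Candidates screened one at a time at 0.2: mean odds ratio as low as 1.02-1.05, with 41-63% coverage in the worst cases.
- Probe number forced in: coverage about 95%.

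**Price of forcing it in.** In set B the standard error for power rose by about 10-40%. In set A the variance inflation factors were 1.46 and 2.77. Their square roots are 1.21 and 1.66, or 21% and 66% wider.

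**The case against.** The strongest reply is that nothing in the documents has power entering a model alone. Probe number and type belong to the same parameter group and are equally eligible. A reader might infer from 11.2 and 8.10 that the planned models take per-probe power as a stand-alone exposure, or that the power result will largely compare one-probe with multi-probe procedures. The documents do not support either reading: the SAP leaves the specification open. The figures for always omitting probe number describe an analysis nobody has planned. If probe number is tested jointly with power, the average estimate after selection is close to the truth.

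That reply stands as far as average bias under joint selection goes. It does not dispose of the point. The SAP does not say that selection is joint, and univariable screening is allowed by its wording and performs much worse. Even under joint selection, the replicates that drop probe number are biased and report intervals that are too short.

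It is also fair that the limits are assumed, and that 11.2 does not say per-probe Watts fall as probes are added. Nor is the direction known. A reader might infer that the power effect must shrink or vanish, but it is inflated if multi-probe cases do worse and unaffected if probe number has no effect of its own.

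Finally, these analyses are labelled exploratory, and the descriptive estimates of the primary endpoints are untouched. That limits the severity. But relating parameters to outcomes is the registry's primary objective (Protocol 6.1), and 8.10 is where the SAP models it.

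**Conclusion.** The point holds as a gap in specification. The device ties power to probe number and type, and SAP 8.10 has a selection rule that can separate them. Where it does, the power estimate can be confounded in either direction and its interval is too narrow.

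The size cannot be fixed from the documents. Under the assumed limits, omitting probe number ranges from no bias, through loss of most of the effect (0.30 to 0.04), to about a doubling (0.30 to 0.61). After selection at 0.2, the harm runs from slight to interval coverage of 41-63%, depending mainly on the selection procedure, which the SAP does not name. These figures rest on assumed limits, probe mix and effects, and cover probe number only; type was not simulated. The change is worth making before the models are run, but the primary descriptive results do not depend on it.

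**What to change.** In SAP 8.10, state that number of probes (as categories) and probe type are kept in every logistic or Cox model that contains power, exempt from the 0.2 rule. Both are already collected (Protocol 19.1 k and l), so only SAP wording changes.

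The cost is a few degrees of freedom and a wider interval for power: about 10-40% in set B, and 21% or 66% in set A. Much of that width is a fair statement of how little the data say about power at a fixed configuration.

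Three tempting additions are not recommended:
- Power relative to the generator limit needs the limit for each configuration, which is not among the 19.1 items.
- Watts times seconds is not delivered energy where power is ramped (19.1 o), and duration (19.1 c) is recorded per ablation attempt, not per probe.
- Separate single-probe and multi-probe models would split few failures: at an assumed 94% success, 0.06 × 1,500 = 90.
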